- concomitant medications, and SOFA score, should be collected daily while hospitalized including any day after Day 8 that the patient remains in the hospital. Results Assessments (including NEWS2, vital signs, severity of COVID-19, subjective symptoms of COVID-19, SpO2, WHO Ordinal Scale for Clinical Improvement, AEs, concomitant medications). For this study, all enteral nutrition and administration of blood products will also be considered as medication. will be collected on an Unscheduled Visit eCRF.

APPENDIX B. QUESTIONNAIRE SCORING

B.1 NATIONAL EARLY WARNING SCORE 2 (NEWS2)

The NEWS-2 is based on a simple aggregate scoring system in which a score is allocated to physiological measurements when participants present to, or are being monitored in hospital. Six simple physiological parameters form the basis of the scoring system:

- Respiration Rate (0-3)
- Oxygen Saturation (0 3)
- Systolic Blood Pressure (0 3)
- Pulse Rate (0-3)
- Level of consciousness or new confusion (0-3)
- Temperature (0-3)

| Physiological | | | | | | | |
|-----------------------------------|-------|--------|-----------|---------------------|--------------------|--------------------|------------------|
| parameter | 3 | 2 | 1 | 0 | 1 | 2 | 3 |
| Respiration rate (per minute) | ≤8 | | 9–11 | 12–20 | | 21–24 | ≥25 |
| SpO ₂ Scale 1 (%) | ≤91 | 92–93 | 94–95 | ≥96 | | | |
| SpO ₂ Scale 2 (%) | ≤83 | 84–85 | 86–87 | 88–92 ≥93 on air | 93–94 on oxygen | 95–96 on oxygen | ≥97 on oxygen |
| Air or oxygen? | | Oxygen | | Air | | | |
| Systolic blood pressure (mmHg) | ≤90 | 91–100 | 101–110 | 111–219 | | | ≥220 |
| Pulse (per minute) | ≤40 | | 41–50 | 51–90 | 91–110 | 111–130 | ≥131 |
| Consciousness | | | | Alert | | | CVPU |
| Temperature (°C) | ≤35.0 | | 35.1–36.0 | 36.1–38.0 | 38.1–39.0 | ≥39.1 | |

A score is allocated to each parameter as they are measured, with the magnitude of the score reflecting how extremely the parameter varies from the norm. The score is then aggregated and uplifted by 2 points for people requiring supplemental oxygen to maintain their recommended oxygen saturation. The higher the NEWS, the more critical is the state of the participant.

B.2 SEQUENTIAL ORGAN FAILURE ASSESSMENT (SOFA) SCORE

The SOFA score is based on a simple aggregate scoring system in which a score is allocated to the following six simple physiological parameters:

- Respiration (0-4)
- Coagulation (0-4)
- Liver (0 4)
- Cardiovascular (0-4)
- Central Nervous System (0 4)
- Renal (0 4)

| SOFA score | 0 | 1 | 2 | 3 | 4 |
|--|------|-----------------|---|----------------------|-----------------|
| Respiration ^a | | | | | |
| PaO ₂ /FIO ₂ (mm Hg) | >400 | 301-400 | 201 - 300 | 101 – 200 | ≤100 |
| Coagulation | | | | | |
| Platelets (×10 ³ /mm ³) | >150 | 101 - 150 | 51-100 | 21 - 50 | ≤20 |
| Liver | | | | | |
| Bilirubin (mg/dL) | <1.2 | 1.2 - 1.9 | 2.0 - 5.9 | 6.0 - 11.9 | ≥12.0 |
| Cardiovascular ^b | | | | | |
| Hypotension | None | MAP <70 mmHg | Dopamine ≤5 or dobutamine (any dose) ^a | Dopamine >5 | Dopamine >15 |
| Central Nervous System | | | | | |
| Glasgow Coma Score | | 13 - 14 | 10-12 | 6-9 | <6 |
| Renal | | | | | |
| Creatinine (mg/dL) or urine output (mL/d) | <1.2 | 1.2 - 1.9 | 2.0-3.4 | 3.5 – 4.9 or <500 | >5.0 or <200 |

 FIO_2 , fraction of inspired oxygen; PaO₂, partial pressure of oxygen; MAP, mean arterial pressure; SaO₂, peripheral arterial oxygen saturation ^a Vasoactive mediations administered for at least 1 hr (dopamine and norepinephrine μ mg/kg/min)

A score is allocated to each parameter as they are measured, with the magnitude of the score reflecting how extremely the parameter varies from the norm. The score is then aggregated. The higher the SOFA score, the more critical is the state of the participant.

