# APPENDIX 3 SEQUENTIAL ORGAN FAILURE ASSESSMENT (SOFA) SCORE

SOFA score	0	1	2	3	4
Respiration					
PaO 2 /FIO 2 (mmHg)	> 400	301-400	201-300	101-200	≤ 100
(kPa)	> 5.3)	(4.1-5.3)	(2.8-4.0)	(1.4-2.7)	≤ 1.3)
Coagulation Platelets (x10  /mm  )	> 150	101-150	51-100	21-50	≤ 20
Liver					
Bilirubin (mg/dl)	< 1.2	1.2-1.9	2.0-5.9	6.0-11.9	≥ 12.0
(µmol/l)	< 20)	(20-32)	(33-101)	(102-204)	≥ 204)
Cardiovascular					
Hypotension	No hypotension	MAP < 70 mmHg	Dopamine ≤ 5 or dobutamine (any dose)*	Dopamine > 5	Dopamine > 15
Central nervous system					
Glasgow coma score	15	13-14	10-12	6-9	< 6
Renal					
Creatinine (mg/dl)	< 1.2	1.2-1.9	2.0-3.4	3.5-4.9	> 5.0
(µmol/l)	< 110)	(110-170)	(171-299)	(300-440)	> 440)
or urine output				< 500 ml/day	< 200 ml/day

\* adrenergic agents administered for at least 1 h (doses given are in µg/kg/min)

Source: de Mendonça et al., 2000

FIO2=fraction of inspired oxygen; PaO2=partial pressure of oxygen.

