4.2.2 Exploratory Efficacy Endpoints

The following are the exploratory efficacy endpoints of Part 1 of this study:

- Mean change from baseline in the NEWS-2 total score on Day 15
- Mean number of days on rescue treatment (COVID-19 therapies that are FDA approved or have emergency-use authorization) within 15 days after enrollment.
- Median time (in days) to resolution of subjective symptoms assessed by the Investigator to be potentially due to COVID-19 including: fever, cough (productive or non-productive), sore throat, malaise, headache, muscle pain, gastrointestinal symptoms (i.e., nausea, vomiting, or diarrhea), shortness of breath (with or without exertion), and respiratory distress
- Proportion of participants who's COVID-19 progresses to Severe or Critical within 15 days after enrollment
- Proportion of participants requiring ICU admission within 15 days after enrollment
- Mean change from baseline in SOFA score on Days 8 and 15
- Proportion of participants on Days 8 and 15 requiring:
 - Supplemental oxygen
 - High flow nasal cannula (HFNC) oxygen
 - Non-invasive positive pressure ventilation (NIPPV)
 - Mechanical ventilation
- Mean number of days on mechanical ventilation within 15 days after enrollment
- Mean number of oxygenation-free days within 15 days after enrollment

- Proportion of participants who achieve a score of 1 on the WHO Ordinal Scale for Clinical Improvement on Days 8 and 15
- Median time (in hours) to a 2-point improvement in the WHO Ordinal Scale for Clinical Improvement
- Incidence and severity of thromboembolic events within 15 days after enrollment
- Incidence of abnormal markers of inflammation to include CRP, IL-6, TF, MCP-1, and IP-10 on Day 8
- Mean change in viral load from baseline on Days 1, 4, 8, 15, and 28
- Median number of days to viral load undetectable by nasopharyngeal (NP) swab

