7.5.6 Sequential Organ Failure Assessment (SOFA) Score

The Sequential Organ Failure Assessment (SOFA) will be administered for all participants who get admitted to ICU. The SOFA will be scored according to authors' instructions (Appendix B.2). For participants who get discharged from ICU before Day 8 or Day 15, their last available SOFA score will be carried forward to Day 8 or Day 15, respectively.

Mean observed and mean change from baseline in SOFA score at Days 8 and 15 will be tabulated by treatment group. Additionally, the difference in the least-squares means and their standard errors adjusted for baseline SOFA score, stratification factors, WHO Ordinal Scale for Clinical Improvement score, and number of co-existing conditions will be tabulated. Corresponding 95% confidence interval of the difference between two least-squares means will also be reported.

Participants who did not get admitted to ICU will not contribute to this analysis.

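### As printed, the SOFA cardiovascular row gives 2 to 4 points only for dopamine or dobutamine, although the footnotes cover other agents; the protocol's kPa row is also about ten-fold too low

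*SAP*

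**What the plan says.** Protocol Appendix 3 and SAP Appendix B.2 print the same cardiovascular row. Score 0 is no hypotension and score 1 is MAP below 70 mmHg. Score 2 is "Dopamine ≤ 5 or dobutamine (any dose") in the protocol and "Dopamine ≤5 or dobutamine (any dose") in the SAP. Scores 3 and 4 are dopamine above 5 and above 15. No cell names norepinephrine or any other vasopressor.

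The footnotes are wider than the cells. The protocol's reads "adrenergic agents administered for at least 1 h (doses given are in µg/kg/min"). The SAP's begins "Vasoactive mediations administered for at least 1 hr (dopamine and norepinephrine" and ends with a unit printed as μ mg/kg/min.

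SAP 7.5.6 makes the table the working rule: "The SOFA will be scored according to authors' instructions (Appendix B.2"). SAP 4.2.2 lists the endpoint as exploratory: "Mean change from baseline in SOFA score on Days 8 and 15". SAP 7.5.6 adds: "Participants who did not get admitted to ICU will not contribute to this analysis".

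In the respiration row, protocol Appendix 3 prints kPa cut-offs of >5.3, 4.1-5.3, 2.8-4.0, 1.4-2.7 and ≤1.3 beneath the mmHg cut-offs >400, 301-400, 201-300, 101-200 and ≤100. The SAP table gives mmHg only.

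**The concern.** A footnote that sets a dose unit for norepinephrine implies a norepinephrine threshold somewhere in the table, and there is none. A programmer working from Appendix B.2 has no rule that gives such a participant more than 1 cardiovascular point.

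This conflicts with the protocol's own view of severity. Appendix 4 counts shock, including a need for vasopressors, as critical illness, and Section 5.4 (criterion 3) excludes it at screening. Enrolled participants should therefore start without vasopressors, so the gap falls mainly on post-baseline scores and would not cancel in a change from baseline. After baseline, SOFA is collected only in ICU (protocol Table 1 footnotes and Section 6.3.2). At stake is whether the SOFA change can show this kind of deterioration at all.

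The kPa row is a separate fault in the same appendix: its two unit rows cannot both be right.

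**Working it through.** **Cardiovascular row, applied literally.** The inputs are the cells of SAP B.2, which match protocol Appendix 3. MAP of 70 mmHg or above without dopamine or dobutamine is read as no hypotension.

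- Dopamine >15: score 4
- Dopamine >5: score 3
- Dopamine ≤5, or any dobutamine: score 2
- None of these, MAP <70 mmHg: score 1
- None of these, MAP ≥70 mmHg: score 0

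For a participant on norepinephrine alone:

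| MAP (mmHg) | Cardiovascular score as printed |
|---|---|
| 60 | 1 |
| 69 | 1 |
| 70 | 0 |
| 85 | 0 |

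The norepinephrine dose plays no part, because no cell refers to it. The same holds for any other vasopressor given without dopamine or dobutamine. A participant whose pressure is brought back to 70 or above by the drug scores the same as one who needs no drug.

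**kPa row.** The formula is kPa = mmHg × 0.133322, a physical constant that is not taken from the documents. The inputs are the mmHg and kPa cut-offs in protocol Appendix 3. The printed kPa figures are not reproduced:

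| mmHg cut-off | Printed kPa | Converted kPa | Converted ÷ printed |
|---|---|---|---|
| 400 | 5.3 | 53.33 | 10.06 |
| 301 | 4.1 | 40.13 | 9.79 |
| 300 | 4.0 | 40.00 | 10.00 |
| 201 | 2.8 | 26.80 | 9.57 |
| 200 | 2.7 | 26.66 | 9.88 |
| 101 | 1.4 | 13.47 | 9.62 |
| 100 | 1.3 | 13.33 | 10.26 |

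The row is low by a factor of ten throughout, apart from rounding. Read back, 5.3 kPa is 5.3 ÷ 0.133322 = 39.8 mmHg.

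Scoring example ratios on each row shows what would happen at a site that used kPa:

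| PaO2/FiO2 (mmHg) | Same value in kPa | Score, mmHg row | Score, printed kPa row |
|---|---|---|---|
| 80 | 10.7 | 4 | 0 |
| 100 | 13.3 | 4 | 0 |
| 150 | 20.0 | 3 | 0 |
| 250 | 33.3 | 2 | 0 |
| 350 | 46.7 | 1 | 0 |
| 450 | 60.0 | 0 | 0 |

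**The case against.** **The endpoint carries little weight.** SOFA change is exploratory in both parts and outside the hierarchical testing in protocol 9.7. The SAP covers Part 1 only: 60 participants, with no formal inference planned (protocol 9.3). SAP 7.5.6 asks for a confidence interval but no p-value. Need for vasopressors is also captured elsewhere, through the critical category in the progression endpoint (SAP 7.5.4) and the medication records (protocol 7.4). All of this stands and sets the severity.

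**The reference to the authors' instructions might let in the source's own rules.** It might, but the sentence points to Appendix B.2, which has no such rule. The contradiction with the footnote remains.

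**Part of the SAP table may be missing from the copy read.** The cardiovascular label carries a marker b with no footnote b, the Glasgow cell for score 0 is blank, and an abbreviation is defined that the table never uses. These signs call for a check against the original. The protocol table is set separately and shows the same dopamine and dobutamine row, so loss of text is an unlikely explanation.

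**A reader might infer that each affected participant loses 1 to 4 of the 24 SOFA points** (2 − 1 = 1 up to 4 − 0 = 4). That assumes norepinephrine should score 2 to 4. No document gives it a score or a threshold, so the range is conditional on a source not included in them.

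**A reader might also infer a bias for or against ANA001.** The rule is the same in both blinded arms, so no direction is shown. What can be said is that a between-arm difference in shock treated only with these other vasopressors would not show in the cardiovascular component beyond the step from 0 to 1.

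**The kPa row has no shown route into the analysis.** The SAP scores in mmHg, the planned sites are in the US, and protocol 6.3.2 has sites record PaO2 and FiO2 themselves for intubated patients. This stands: the row is wrong, but its practical effect is probably small.

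**Conclusion.** Both faults are real as printed, and both are minor.

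The cardiovascular row is a scoring definition that does not match its own footnotes. Taken literally, it caps a participant on norepinephrine or another vasopressor alone at 1 of 4 cardiovascular points, and gives 0 once MAP reaches 70 mmHg. The under-scoring falls mainly on post-baseline values because shock is excluded at entry. This rests on Appendix B.2 being the rule actually programmed and on the printed row being complete. The exact points lost and the number of participants affected cannot be derived from the documents.

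The kPa row is wrong by a factor of about ten in every cell. It can cost up to 4 respiratory points, but only for a participant scored from kPa, and the documents do not show that any site would do so.

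The primary endpoint and the sample size are unaffected.

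**What to change.** 1. In protocol Appendix 3 and SAP B.2, reconcile the cardiovascular cells with the footnotes by completing the cells from the scoring source that Appendix 3 cites. Take the entries from that source; none is proposed here.
2. Use the protocol's unit, µg/kg/min, in both tables and correct the SAP footnote, whose printed unit cannot be used. Resolve the unmatched b marker and the blank Glasgow cell at the same time.
3. State in SAP 7.5.6 that the cardiovascular score is derived from vasopressor name, dose and duration. Protocol 7.4 already requires these on the eCRF. Check that the recorded dose can be expressed per kg per minute; weight is collected on Day 1.
4. Correct the kPa row to >53.3, 40.1-53.3, 26.8-40.0, 13.5-26.7 and ≤13.3, or delete it as the SAP does.

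The cost is two table corrections, one sentence in the SAP and a data-capture check. No new procedure or visit is needed.

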APPENDIX C. POTENTIALLY CLINICALLY SIGNIFICANT LABORATORY CRITERIA

| Local Laboratory | | | | | | | | | |
|----------------------------------|--------------------|----------------|-----------------|------------------------|------------------------|--|--|--|--|
| Parameter | SI Unit | Lower Limit | Higher Limit | % Decrease from BSL | % Increase from BSL | | | | |
| CHEMISTRY | | | | | | | | | |
| Blood urea nitrogen (BUN) | mmol/L | NA | >1.5*ULN | NA | >100 | | | | |
| Creatinine | mg/dL | NA | >1.5*ULN | NA | >50 | | | | |
| Sodium | mmol/L | <0.85*LLN | >1.1*ULN | >10 | >10 | | | | |
| Potassium | ∫mol/L | <0.8*LLN | >1.2*ULN | >20 | >20 | | | | |
| Chloride | mmol/L | <0.8*LLN | >1.2*ULN | >20 | >20 | | | | |
| Carbon dioxide (Bicarbonate) | | <0.7*LLN | >1.3*ULN | >40 | >40 | | | | |
| Glucose | mmol/L | <0.6*LLN | >3.0*ULN | >40 | >200 | | | | |
| Total bilirubin | mg/dL | NA | >2.5*ULN | NA | >150 | | | | |
| Direct bilirubin | mg/dL | NA | >1.5*ULN | NA | >150 | | | | |
| Alkaline Phosphatase | U/L | <0.5*LLN | >2.0*ULN | >80 | >100 | | | | |
| Aspartate Aminotransferase (AST) | U/L | NA | >3.0*ULN | NA | >200 | | | | |
| Alanine Aminotransferase (ALT) | U/L | NA | >3.0*ULN | NA | >200 | | | | |
| HEMATOLOGY | | | | | | | | | |
| Hematocrit | Ratio | <0.8*LLN | >1.3*ULN | >20 | >30 | | | | |
| Hemoglobin | g/L | <0.8*LLN | >1.3*ULN | >20 | >30 | | | | |
| Platelet Count | 10 ⁹ /L | <0.65*LLN | >1.5*ULN | >50 | >100 | | | | |
| White Blood Cell Count | 10 ⁹ /L | <0.65*LLN | >1.6*ULN | >60 | >100 | | | | |
| Neutrophils, absolute cell count | 10 ⁹ /L | <0.65*LLN | >1.6*ULN | >75 | >100 | | | | |
| Lymphocytes, absolute count | 10 ⁹ /L | <0.25*LLN | >1.5*ULN | >75 | >100 | | | | |
| Eosinophils, absolute count | 10 ⁹ /L | NA | >4.0*ULN | NA | >300 | | | | |
| Monocytes, absolute count | 10 ⁹ /L | NA | >4.0*ULN | NA | >300 | | | | |

| Basophils, absolute count | 10 ⁹ /L | NA | >4.0*ULN | NA | >300 | | | |
|--------------------------------------|--------------------|----------|----------|------|------|--|--|--|
| COAGULATION | | | | | | | | |
| Partial thromboplastin time (aPTT) | sec | <0.5*LLN | >2.0*ULN | >100 | >100 | | | |
| Prothrombin time (PT) | sec | <0.5*LLN | >2.0*ULN | >100 | >100 | | | |
| International normalized ratio (INR) | Ratio | <0.5*LLN | >2.0*ULN | >100 | >100 | | | |

LLN: Lower limit of normal value provided by the local laboratory ULN: Upper limit of normal value provided by the local laboratory BSL: Baseline

| Parameter | SI Unit | Lower Limit | Higher Limit | % Decrease from BSL | % Increase from BSL | | |
|--------------------|---------|----------------|-----------------|------------------------|------------------------|--|--|
| ADDITIONAL TESTING | | | | | | | |
| D-Dimer | ng/mL | NA | >1.0*ULN | NA | >20 | | |
| Cardiac troponin | ng/mL | NA | >1.0*ULN | NA | >30 | | |
| Ferritin | ng/mL | NA | >1.2*ULN | NA | >30 | | |
| LDH | U/L | <0.4*LLN | >4.0*ULN | >60 | >300 | | |
| CRP | mg/dL | <1.0*ULN | >1.3*ULN | >80 | >50 | | |

Central Laboratory Results

LLN: Lower limit of normal value provided by the local laboratory ULN: Upper limit of normal value provided by the local laboratory BSL: Baseline

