7.5.10 Inflammation Markers Associated with Acute Respiratory Distress Syndrome (ARDS)

The following inflammation markers associated with acute respiratory distress syndrome will be analyzed at a central lab: CRP, IL-6, TF, MCP-1, and IP-10. An inflammation marker is considered abnormal if the reported value is > ULN.

Incidence of abnormal inflammation markers at Day 8 will be tabulated by treatment group and compared in a way similar to the analysis of ICU Admissions in Section 7.5.5.

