7.6.2 Clinical Laboratory Evaluation

Laboratory parameters will be summarized by treatment group at each visit. Each summary will include the values of the laboratory parameters and their change from baseline. Shift tables from baseline will be presented for laboratory values in the chemistry and hematology panels that are captured categorically. Parameters will be classified as potentially clinically significant according to the criteria described in Appendix C. In addition, the laboratory results will be

graded by CTCAE v5.0 and the summary of treatment-emergent laboratory results by highest CTCAE grade will be summarized.

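### SAP Appendix C sets the low CRP limit at the upper limit of normal, so a CRP that normalises from a high baseline is classed as potentially clinically significant

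*SAP*

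**What the plan says.** SAP 7.6.2 makes Appendix C the operative rule: "Parameters will be classified as potentially clinically significant according to the criteria described in Appendix C". It does not exempt the central-laboratory rows. SAP 4.3 lists the incidence of treatment-emergent PCS laboratory abnormalities among the safety endpoints.

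The CRP limits in Appendix C are "CRP | mg/dL | <1.0*ULN | >1.3*ULN", and the full row is "CRP | mg/dL | <1.0*ULN | >1.3*ULN | >80 | >50". The columns are lower limit, higher limit, percentage decrease from baseline and percentage increase from baseline. The legend under the table reads "ULN: Upper limit of normal value provided by the local laboratory".

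Two rows of the same table serve as comparators. LDH, directly above CRP, has a lower limit built on LLN: "LDH | U/L | <0.4*LLN | >4.0*ULN | >60 | >300". Ferritin has no low-side criterion at all: "Ferritin | ng/mL | NA | >1.2*ULN | NA | >30". D-dimer and cardiac troponin likewise carry NA for both the lower limit and the percentage decrease.

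SAP 7.5.10 names CRP among the inflammation markers and states: "An inflammation marker is considered abnormal if the reported value is > ULN".

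In the coagulation block the first row is "Partial thromboplastin time (aPTT) | sec | <0.5*LLN | >2.0*ULN | >100 | >100". PT and INR have the same entries.

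**The concern.** A low-side safety limit should pick out values that are unusually low. Here it is placed at the top of the normal range, so the low flag catches normal values. CRP is drawn on Days 1, 4 and 8 (Protocol Table 1; SAP Appendix A), and the protocol synopsis hypothesises that ANA001 reduces inflammation. The change the sponsor hopes to see, a raised CRP coming down to normal, would then be recorded as a PCS abnormality in a safety table. The same normal Day 8 result would be not abnormal in the exploratory marker analysis and PCS in the safety output. A programmer who follows the SAP exactly would produce this result.

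**Working it through.** The plan states no figure to reproduce. The check applies the Appendix C row to CRP values.

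**Inputs from SAP Appendix C.** Low limit below 1.0 × ULN, high limit above 1.3 × ULN, decrease above 80%, increase above 50%.

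**Assumptions.** Baseline *b* and follow-up *x* are illustrative values in multiples of ULN. The documents give no CRP distribution, and no inclusion criterion requires a raised CRP.

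**Formula.** Percentage decrease D = 100 × (b − x)/b.

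**Three readings**, because the SAP gives no combining rule:
- Limits alone: flag if x < 1.0 or x > 1.3.
- OR: flag if x < 1.0, or x > 1.3, or D > 80, or the increase exceeds 50%.
- AND: flag if x < 1.0 and D > 80, or if x > 1.3 and the increase exceeds 50%.

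| Baseline → follow-up (× ULN) | Change | Limits alone | OR | AND |
|---|---|---|---|---|
| 10 → 0.9 | −91% | low | low, decrease | low |
| 5 → 0.9 | −82% | low | low, decrease | low |
| 3 → 0.9 | −70% | low | low | none |
| 0.8 → 0.8 | 0% | low | low | none |
| 10 → 1.1 | −89% | none | decrease | none |
| 10 → 10 | 0% | high | high | none |

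**Limits alone.** Only 1.0 to 1.3 × ULN escapes a flag, so a mildly raised CRP passes and a normal one does not.

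**AND.** D > 80 is the same as x < 0.2b. The share of the range below ULN that is flagged is therefore min(1, 0.2b):
- b = 2: 0.2 × 2 = 40%
- b = 3: 0.2 × 3 = 60%
- b = 5 or more: 100%

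From 5 × ULN upward, every return to below ULN is flagged under all three readings. Under AND, a CRP that stays at 10 × ULN is not flagged, while one that falls from 10 to 0.9 is.

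**Testing repairs on 10 → 0.9 (D = 91):**
- Replace ULN by LLN only, with LLN assumed between 0 and 0.1 × ULN: no flag on limits alone or under AND, but still flagged under OR because 91 > 80.
- Set the lower limit and the percentage decrease both to NA: no flag under any reading.

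**Coagulation rows.** For a positive follow-up value, D = 100 × (1 − x/b) is always below 100, so a decrease of more than 100% cannot occur. Under OR the cell does nothing, and values below 0.5 × LLN are still caught. Under AND the low flag for aPTT, PT and INR can never fire.

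**The case against.** The strongest reply is that this looks like one mistyped cell in a descriptive table for a secondary marker. Much of that stands. SAP 7.6 says safety data are summarised descriptively without inference, Part 1 has 60 participants, and the laboratory criteria for DMC action in Protocol 6.6.2 concern anemia, neutropenia and thrombocytopenia, not CRP. SAP 7.6.2 also tabulates observed values and change from baseline, so a falling CRP would be visible as such. A substitution of ULN for LLN is plausible but cannot be confirmed from the documents.

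A reader might infer four stronger things that the documents do not support:

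- *That every normal CRP is counted as an abnormality.* This needs limits alone or OR, and the SAP states neither. Under AND an unchanged normal CRP is not flagged. The endpoint also counts treatment-emergent abnormalities, so a value already below ULN at baseline may not count as new.
- *That the comparison between arms is reversed, with recovery counted as harm.* Patients who stay above 1.3 × ULN are flagged high on limits alone or under OR. If low and high flags are pooled, most participants in both arms could be flagged and the table says little. If they are shown separately, the low row can be read for what it is. Reversal depends on treatment-emergent and pooling rules that the SAP does not give.
- *That the Part 1 primary endpoint is corrupted.* SAP 4.2 and the protocol name hematology, chemistry and coagulation. Protocol Appendix 5 lists CRP among additional central tests, without the mark for tests used mainly in safety summaries. The wording of SAP 4.3 does not shut CRP out, but nothing names it.
- *That the two SAP sections must use one threshold.* An exploratory marker cut-off and a PCS cut-off may differ. Only the low CRP cell conflicts with 7.5.10.

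What the reply does not remove is that normalisation from a high baseline is PCS under every reading of the row.

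**Conclusion.** The point holds as a specification error of limited reach. As written, Appendix C classes a CRP that normalises from 5 × ULN or more as PCS, whichever way the columns are combined. On limits alone or under OR it also classes any other value below ULN as PCS. This conflicts with SAP 7.5.10 and makes the CRP PCS tabulation uninformative or misleading. The baseline multiples are illustrative, so no count of affected participants can be given. The effect stays within a descriptive Part 1 laboratory table for a marker outside the named panels, and no test or stopping criterion in the documents uses it. The coagulation entry is secondary: harmless under OR, but it disables the low flag for a named safety panel under AND. The correction should be made before the Part 1 tables are produced.

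**What to change.** In SAP Appendix C:

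1. Set the CRP lower limit and percentage decrease to NA, matching D-dimer, cardiac troponin and ferritin. Changing ULN to LLN alone is not enough, because under OR the decrease criterion of more than 80% would still flag recovery.
2. Add one sentence saying how the limit and percentage-change columns combine. It would help for the same sentence to say when a laboratory value counts as treatment-emergent.
3. For aPTT, PT and INR, set the percentage decrease to NA or to an attainable value. If the combining rule chosen is AND, check that the entry leaves a working low flag.

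With the first change the conflict with SAP 7.5.10 disappears, and the higher limit of 1.3 × ULN can stay as a separate PCS threshold. The cost is five table cells and a sentence or two in the SAP. Sample size, data collection and the protocol are unaffected.
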